### 1. Abstract

Alcohol use disorders (AUDs) are prevalent among Veterans and result in significant physical and psychological burden. Among those who receive treatment for AUDs, 1 in 3 relapses to problematic drinking within one year of treatment. Thus, additional strategies are needed to enhance alcohol treatment outcomes. One promising approach involves providing concurrent treatment for a common complaint – difficulty falling or staying asleep. Up to 74% of Veterans seeking treatment for AUD report co-occurring symptoms of insomnia. Given the negative impact of insomnia on attention and emotion regulation, insomnia symptoms may decrease patients' abilities to attend to alcohol treatment and manage negative emotions that lead to craving and relapse. Moreover, approximately 50% of individuals with AUDs report using alcohol to help them sleep, making relapse more likely for those with no other tools or skills to help them sleep. Indeed, sleep disturbance has been identified as a risk factor for relapse among individuals in alcohol treatment. Thus, effective treatment of sleep problems may enhance alcohol treatment. Cognitive Behavioral Therapy for Insomnia (CBT-I) has been effective in reducing insomnia severity in individuals with AUDs; however, no investigations have examined the efficacy of CBT-I delivered concurrently with AUD treatment to determine its impact on treatment outcomes. This R21 aims to examine the feasibility, acceptability, and initial efficacy of a CBT-I supplement to outpatient alcohol treatment. A randomized pilot trial with 80 Veterans who meet diagnostic criteria for AUD and Insomnia Disorder will be conducted. Participants will be randomly assigned to receive Cognitive Behavioral Therapy for Insomnia (CBT-I) or minimal treatment (sleep hygiene handout only; SH) in addition to alcohol treatment as usual. Outcomes will be assessed at the end of the active intervention period (6 weeks) and 6 weeks post-intervention. Outcomes of interest include recruitment/retention rates, treatment satisfaction, insomnia severity, use of alcohol as a sleep aid, percentage of heavy-drinking days, and alcohol-related problems. Analyses will focus on size of treatment effects. This study will provide initial evidence that treatment of insomnia not only improves sleep but also allows participants to derive greater benefit from outpatient alcohol treatment.

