Consistent with PA-18-202, the proposed R21 aims to examine the feasibility, acceptability, and initial efficacy of a CBT-I supplement to outpatient alcohol treatment. The **primary objective** of this study is to enhance alcohol treatment to account for the unique needs of Veterans with sleep disorders. We propose a 6-week randomized trial, in which 80 Veterans will be randomly assigned to receive Cognitive Behavioral Therapy for Insomnia (CBT-I) or minimal treatment (sleep hygiene only; SH) in addition to treatment as usual. Individuals participating in the Addictions Treatment Program at the Truman VA will be eligible to participate if they meet DSM-5 criteria for AUD and the episodic criterion ( $\geq 1$  mo) for Insomnia Disorder. Participants will complete assessments at baseline, post-treatment, and 6-week follow-up. We propose the following specific aims:

**Aim 1: To test the feasibility and acceptability of CBT-I delivered concurrently with alcohol treatment.** Recruitment (anticipated enrollment of at least 2 Veterans per month) and retention rates (goal  $\geq 70\%$  complete 6/6 treatment sessions) will indicate feasibility of the intervention. Treatment satisfaction (average score  $\geq 3$ , indicating ‘mostly satisfied’) will serve as an indicator of acceptability. Retention and satisfaction will be measured separately for insomnia and alcohol treatments.

**Aim 2: To evaluate the initial efficacy of CBT-I on insomnia and alcohol use outcomes.** We hypothesize that Veterans receiving CBT-I will demonstrate greater improvements in insomnia severity, sleep efficiency, use of alcohol as a sleep aid, percentage of heavy-drinking days, and alcohol-related problems post-treatment and at 6-week follow-up.

**Aim 3 (exploratory): To examine proximal intervention outcomes.** We hypothesize that Veterans receiving CBT-I will demonstrate greater post-treatment improvements in attention (vigilance), working memory, treatment-related learning, negative affect, and emotion regulation.

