To confirm diagnosis of insomnia, all eligible participants will complete one week of daily sleep diaries (between baseline and treatment session 1), which will be collected electronically and time-stamped each morning using the Qualtrics data management system. Participants who have not completed the diary each morning by noon will receive a reminder text or phone call from study staff. Sleep diaries measure sleep onset latency, wake after sleep onset, total sleep time, sleep efficiency, and sleep quality. In this study, sleep diaries will also assess use of sleep medication and use of alcohol/other drugs (yes/no) to help with sleep. Sleep medication variables will include name, dosage, and time taken and will be converted to lowest recommended dosage units for data analysis. Participants who are unable to complete the daily sleep diaries by computer or phone will be provided with pen-and-paper surveys to fill out each day by hand.

*Follow-up.* Follow-up assessments (see Table 1) will be administered in person by the RA, who will be blind to participant condition. Upon completion of the study, SH participants will be offered a referral for CBT-I, which is available with trained providers at the VA.

*Remote appointments.* If needed, treatment and follow-up appointments may be completed remotely using Zoom Pro or the VA's Video Connect service. Using their VA email from the VA laptops, research staff would send the participant a link to launch the session. Participants wanting to use their iPhone or iPad for the session would have to download the VA Video Connect application onto their device. On all other devices (e.g., PCs, laptops, Android devices), the participant will simply open the email and click the link to launch the secure video session. This service uses encryption to ensure that sessions are private and secure and is designed for Veterans in rural areas with limited access to healthcare facilities.

*Retention strategies.* To enhance follow-up rates, participants will receive:

- Up to \$40 for baseline (~2hr): \$10 for completing the assessment, \$10 for completing all seven daily surveys, and \$20 for returning the actiwatch.
- Up to \$50 for the post-treatment assessment (~1hr): \$40 for completing the assessment and \$10 for completing all seven daily surveys
- Up to \$60 for the 6-week follow-up (~1hr): \$50 for completing the assessment and \$10 for completing all seven daily surveys

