Use	Construct	Measure(s)	BL	Post	6wk
Cov	Demographics	See instruments	X		
	Other drug use , past 6 weeks	Drug Use Screening Inventory	X	X	X
	Use of sleep medication	Daily Sleep Diary (Carney et al., 2012)	X	X	X
Aim 1	Recruitment	Completion of ≥ 1 session of CBT-I		X	
	Retention	Completion of 6/6 sessions of CBT-I		X	
	Treatment satisfaction , measured separately for CBT-I and CBT-AUD	Client Satisfaction Questionnaire (Larsen et al., 1979)			X
Aim 2	% abstinent days , past 6 weeks	Timeline Follow-back (TLFB) for alcohol (Sobell & Sobell, 1996)	X	X	X
	% heavy-drinking days (≥4/5 drinks/day for women/men)				
	Alcohol problems , past 6 weeks	Short Inventory of Problems ([name] et al., 1995)	X	X	X
	Use of alcohol or other drugs to help with sleep , past 6 weeks	Daily Sleep Diary (Carney et al., 2012)	X	X	X
	Insomnia severity , past 2 weeks	Insomnia Severity Index (Morin et al., 2011)	X	X	X
	Total wake time , average past week	Daily Sleep Diary (Carney et al., 2012)	X	X	X
	Sleep quality , average past week	Daily Sleep Diary (Carney et al., 2012)	X	X	X
	Dysfunctional beliefs, past month	Dysfunctional Beliefs about Sleep Scale	X	X	X
Aim 3	Treatment-related learning	Project SAVE Alcohol Quiz Project SAVE Alcohol Vignette	X	X	X
	Executive functioning	Psychomotor Vigilance Task (Dinges et al., 1985) N-back Task (Schmiedek et al., 2014) Monetary Choice Questionnaire UPPS Measure of Impulsivity Cognitive Failures Questionnaire	X	X	X
	Negative affect , past week	Positive and Negative Affect Schedule	X	X	X
	Emotion regulation , past 30 days	Brief Difficulties in Emotion Regulation Scale (Bjureberg et al., 2016)	X	X	X
	Alcohol craving , past week	Penn Alcohol Craving Scale	X	X	X
	Mental health symptoms	PTSD Checklist for DSM-5 Patient Health Questionnaire-9 for depression GAD-7 measure of anxiety Satisfaction with Life Scale	X	X	X

*Note.* BL=baseline. Cov = potential covariates. Post = post treatment. Wk = week.

*Blinding.* PI [name] will not be blinded to block size or participant assignment because she will inform study therapists of participant assignment to conditions. However, PI [name] and study therapists will be blinded to assessment outcomes, and the assessment RA will be blinded to participant condition.

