## **7. Study Statistics**

*Outcome measures.* Outcome measures are listed in Table 1 above. Primary outcomes include recruitment, retention, and treatment satisfaction (Aim 1) as well as insomnia severity, total wake time, sleep quality, percent days abstinent, percent heavy-drinking days, alcohol problems, and use of alcohol or other drugs as a sleep aid (Aim 2). Secondary (Aim 3) outcomes include treatment-related learning, executive function (attention, working memory, delayed discounting, impulsivity), negative affect, emotion regulation, craving, and mental health symptoms (PTSD, depression, anxiety, life satisfaction).

*Aim 1 analyses.* Recruitment (goal  $\geq 4$  pts/mo) and retention rates ( $\geq 70\%$  complete 5/5 sessions) will indicate feasibility of the intervention. Treatment satisfaction (average score  $\geq 3$ , indicating ‘good’ quality) will serve as an indicator of acceptability. Recruitment, retention, and satisfaction will be measured separately for insomnia and alcohol treatments. We do not expect group differences in recruitment. Descriptive statistics, chi-square, and t-tests will be used to determine between-group differences in retention and satisfaction.

*Aims 2-3 analyses.* Cohen’s  $d$  (adjusted for baseline scores) and 95% CIs will be used to examine the magnitude of between-group differences at post-treatment and 6-week follow-up. We will use HLM to compare conditions at post-treatment and 6 weeks. We chose HLM over other statistical approaches (e.g., ANOVA) because it requires fewer assumptions, has superior ability to handle missing data, and will yield greater

statistical power. In each model, the Level 1 variable will be time. Level 2 portions of the model will include the effect of condition. Hypotheses will be tested by regressing condition on the Level 1 intercept and time effect. Analyses will be intent-to-treat. We will examine whether attrition is associated with any baseline variables and control for such variables when necessary.

*Power analysis.* Post-hoc power analyses conducted in G\*Power 3.0.10 indicate that 80 participants will provide strong power ( $1 - \beta = .99$ ) to detect within-between interactions of moderate magnitude ( $f = .25$ ).

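### Aim 2 predicts less drinking to get to sleep, but its primary outcome pools alcohol with other drugs, and the plan does not say whether the diary separates them

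*Combined protocol and SAP*

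**What the plan says.** Two places state the hypothesis in terms of alcohol alone.

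- Abstract: the outcomes of interest include "insomnia severity, use of alcohol as a sleep aid, percentage of heavy-drinking days, and alcohol-related problems".
- Section 3, Aim 2: the CBT-I arm is expected to show "greater improvements in insomnia severity, sleep efficiency, use of alcohol as a sleep aid, percentage of heavy-drinking days".

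Three places define or name the outcome, and all pool alcohol with other drugs.

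- Section 4, baseline assessment: "sleep diaries will also assess use of sleep medication and use of alcohol/other drugs (yes/no) to help with sleep".
- Section 4, Table 2, Aim 2 row: "Use of alcohol or other drugs to help with sleep", with the Daily Sleep Diary as the only instrument.
- Section 7, outcome measures: the primary outcomes include "percent days abstinent, percent heavy-drinking days, alcohol problems, and use of alcohol or other drugs as a sleep aid (Aim 2".

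The yes/no format appears only in the Section 4 diary description; Table 2 and Section 7 name a construct without a response format. Prescribed or other sleep medication is handled separately: "Sleep medication variables will include name, dosage, and time taken".

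**The concern.** Drinking in order to sleep is the first of the three reasons that Section 3 gives for treating insomnia as a barrier to alcohol treatment. A primary outcome meant to show movement on that pathway should isolate it. The pooled variable does not: a yes may mean alcohol, another drug, or both.

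Other drug use is a live possibility in this trial. It is not an exclusion in Section 4 or Section 5, and Table 2 lists it as a potential covariate. At stake is the interpretation of the result in either direction. A positive finding might owe nothing to alcohol, and a null finding might conceal a real fall in drinking to sleep.

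**Working it through.** **1. Is there a figure in the plan to reproduce?** None is specific to this outcome. The only power statement (Section 7: N = 80, f = .25, power .99) is general. With noncentrality f² × N × m / (1 − ρ), two groups and an assumed alpha of .05, it gives 0.989 (m = 3 measurements, ρ = .3), 0.999 (m = 3, ρ = .5) and 0.993 (m = 2, ρ = .5). The figure is therefore reproducible under common settings, but the point here does not depend on it.

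**2. How the pooled variable behaves.** Let a be the proportion of nights with alcohol used for sleep and q the proportion with another drug used for sleep, assumed independent. The pooled rate is 1 − (1 − a)(1 − q). The documents give no nightly rates, so all inputs in this step are assumptions: a = .30 in SH and .15 in CBT-I, a true alcohol difference of 15 points.

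*q equal in both arms.* The pooled difference is .15 × (1 − q):

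- q = .10: 13.5 points
- q = .20: 12.0 points
- q = .30: 10.5 points
- q = .40: 9.0 points

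*CBT-I also lowers other-drug nights, .20 to .10.* SH: 1 − .70 × .80 = .440. CBT-I: 1 − .85 × .90 = .235. The difference is 20.5 points, more than the alcohol effect.

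*Alcohol unchanged at .30, other-drug nights .20 to .10.* SH: .440. CBT-I: 1 − .70 × .90 = .370. The pooled variable shows 7 points with no change in alcohol.

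*Other-drug nights rise in CBT-I.* With q = .20 in SH, the pooled difference vanishes when .85 × (1 − q) = .56, that is at q = .341 in CBT-I. If every alcohol night given up becomes an other-drug night (q = 0 in SH), the rates are .30 and .15 + .15 = .30, and the difference is zero.

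**3. What equal-q dilution would do to power.** This takes any use for sleep per participant, 40 per arm, two-sided .05, and a simple comparison of two proportions with pooled variance under the null. It is not the planned HLM. The SH alcohol rate of 50% borrows the Section 3 background figure; the CBT-I rate of 25% and all values of q are assumed.

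| q | SH | CBT-I | Difference (points) | Power |
|---|---|---|---|---|
| 0 (alcohol only) | .500 | .250 | 25.0 | 0.64 |
| .10 | .550 | .325 | 22.5 | 0.53 |
| .20 | .600 | .400 | 20.0 | 0.43 |
| .30 | .650 | .475 | 17.5 | 0.35 |
| .50 | .750 | .625 | 12.5 | 0.22 |

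Between q = 0 and q = .50, power falls from 0.82 to 0.30 if the CBT-I rate is 20%, and from 0.45 to 0.16 if it is 30%.

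**4. Can the other instruments separate the two?** Only in part.

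- The alcohol Timeline Follow-back (Table 2, past 6 weeks, all three assessments) records drinking but not its purpose. It can rule alcohol out on a dry day. It cannot classify a night on which both alcohol and another drug were used.
- The Drug Use Screening Inventory covers the past 6 weeks, and no rule links it to diary nights. In participants reporting no other drug use, a yes points to alcohol; but selecting people on drug use reported after baseline conditions on post-randomisation behaviour.
- Coverage may be incomplete. In Table 1 the seven-survey bonuses fall in weeks 2, 8 and 13, one week after the assessments in weeks 1, 7 and 12. If the diary weeks follow the assessments, as Section 4 describes for baseline, the final one lies after the last Timeline Follow-back.
- None of this is prespecified.

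**The case against.** The diary form is not in the documents. The slash in the diary description could mean one combined question or a separate yes/no for each substance. A reader might infer that there is a single item; the text does not establish that. This stands. But separate answers would not remove the mismatch, because Table 2 and Section 7 would still name the pooled construct as the outcome.

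A reader might also infer that the alcohol hypothesis cannot be tested at all. That goes too far. Even with a combined item, dry days on the Timeline Follow-back and reports of no other drug use allow some yes answers to be attributed. The test would be indirect, incomplete and unplanned, but not impossible.

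Nor does pooling always dilute. The 20.5-point case shows that it can inflate, and equal other-drug use in both arms is only an assumption. Nothing in the documents supports any particular rate of other drugs used for sleep.

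Finally, a pooled outcome can be defended on substance, because it does not credit a participant for swapping alcohol for another drug. This is also one of seven Aim 2 primary outcomes in a pilot focused on effect sizes, and drinking itself is measured separately. These arguments limit the consequence. They do not explain why the hypothesis names one construct and the outcome another.

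**Conclusion.** The point holds as a mismatch between hypothesis and outcome. The hypothesis concerns alcohol; the primary outcome and its only listed measure concern alcohol or other drugs; and the plan is silent on whether the diary distinguishes them. Followed as written, the analysis does not directly test what Aim 2 predicts.

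The size of any distortion is unknown. If other-drug use is equal across arms and independent of alcohol, the alcohol difference shrinks by the factor (1 − q). If other-drug use differs between arms, the pooled difference may be larger than the alcohol difference, smaller, or nil. The mismatch rests on the text alone; the illustrative figures rest on assumed rates. It is worth correcting because the remedy is cheap and, if answers are combined, nights with both substances cannot be resolved later.

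**What to change.** Record alcohol and other drugs as two separate yes/no answers in the diary. Name the alcohol answer as the Aim 2 outcome in Table 2 and Section 7, and keep the pooled variable as a secondary outcome. If the diary already separates them, say so in Section 4 and change only the outcome wording.

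If a combined item is already in use, restate the Aim 2 hypothesis, and the abstract with it, to match the pooled outcome. Prespecify an alcohol-specific sensitivity analysis using Timeline Follow-back days. State that nights with both substances remain ambiguous and that diary weeks falling after an assessment may not be covered.

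The cost is at most one extra yes/no item per diary and small wording edits.

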#### 4. Study Procedures

This study will examine the feasibility, acceptability, and initial efficacy of Cognitive Behavioral Therapy for Insomnia (CBT-I) delivered concurrently with CBT for AUD using a randomized, parallel, two-group design (see Figure 1). Eighty Veterans will be randomly assigned to either **CBT-I** or a sleep hygiene education control (**SH**). All outcomes will be assessed at baseline, post-treatment, and 6-week follow-up. This design will allow us to test the feasibility and acceptability of CBT-I among those in treatment for AUD (**Aim 1**); evaluate the initial efficacy of CBT-I in improving insomnia and alcohol-related outcomes (**Aim 2**); and examine CBT-I effects on attention, working memory, learning, negative affect, and emotion regulation, which may be examined as mediators in a subsequent trial (**Aim 3**).

**Study site.** Participants will be recruited through the Addictions Treatment Program at the Harry S. Truman Memorial Veterans Hospital (Truman VA) in Columbia, MO. We will recruit 115 participants over 20 months (see Table 2) to obtain a final sample of at least 80 participants.

[figure not shown]

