**Recruitment and initial screening.** Patients in the Addictions Treatment Program (ATP) at the Truman VA will be recruited via flyers and provider referral. All residential patients at the ATP will receive a flyer about the study and complete a brief (9-item) screener for the study as part of the intake process. Providers will share the de-identified results of the screener with PI [name]. If participants are interested in the study, they may contact the research team directly. However, to decrease burden on both providers and participants, providers will also have the option of providing the research team with contact information for patients who may be eligible and interested. The research team will then reach out to the patient directly to assess their interest in participating. Research staff will reach out to potential participants three times by phone. Research staff will also attend the beginning of treatment groups/meetings in order to inform individuals about the study and answer any questions they may have. PI [name] will participate in weekly behavioral health team meetings to facilitate the screening and recruitment process (i.e., reminding them about the study, updating them on recruitment progress, and answering any questions).

**Phone screening.** A research assistant (RA) will share more details about the study and conduct a brief eligibility screen ( $\sim 15$ min) with the potential participant in person or over the phone (see Table 1). Those who screen eligible will be scheduled for baseline.

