**Baseline assessment.** Participants will provide written informed consent prior to completion of baseline (see Table 1). In the case of remote baseline assessments, an RA will walk the participant through an electronic version of the written consent form, which they will be asked to sign electronically via the Qualtrics platform. The RA will then print and sign the electronic version of the participant's consent. The baseline evaluation will involve assessment of substance use and sleep disorders and full eligibility criteria using the Mini International Neuropsychiatric Interview (MINI) 7.0.2. Consistent with standard practice, those who endorse symptoms of sleep-related breathing disorders, restless legs syndrome, periodic limb movement disorder, or narcolepsy will be referred for polysomnography. Given the prevalence of sleep apnea in this population, individuals who meet all eligibility criteria but report symptoms of sleep apnea will complete one night of holter monitoring (using an Evo Holter Recorder, SpaceLabs Healthcare) at home in their own beds to rule out for sleep apnea.

Eligible participants will complete baseline assessment measures and will be randomly assigned to either the CBT-I or SH condition. Participants in both conditions will be oriented to the prospective sleep diary, which

they will be asked to complete every morning for the next 6 weeks. The RA will provide all participants with a general handout on sleep hygiene (from the National Sleep Foundation website) and answer any questions they may have about the guidelines.

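### The principal investigator knows the block size and every assignment while helping with recruitment, and no concealment procedure is described, so a share of upcoming allocations is predictable

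*Combined protocol and SAP*

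**What the plan says.** All of the relevant text is in Section 4, Study Procedures.

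- **Blinding.** The principal investigator "will not be blinded to block size or participant assignment because she will inform study therapists of participant assignment to conditions". The same paragraph blinds the investigator and the therapists to assessment outcomes, and states that "the assessment RA will be blinded to participant condition".
- **Recruitment and initial screening.** The principal investigator "will participate in weekly behavioral health team meetings to facilitate the screening and recruitment process". A bracket explains this as reminders, progress updates and answers to staff questions. On the intake screener: "Providers will share the de-identified results of the screener with PI".
- **Phone screening.** Eligibility is screened by someone else: "A research assistant (RA) will share more details about the study and conduct a brief eligibility screen".
- **Randomization.** The design is described as "using a randomized, parallel, two-group design", with the sentence "Eighty Veterans will be randomly assigned to either" CBT-I or sleep hygiene. The baseline paragraph adds: "Eligible participants will complete baseline assessment measures and will be randomly assigned to either the CBT-I or SH condition".

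The protocol does not say who generates the sequence, who holds it, how it is concealed, whether block sizes vary, or who releases each assignment. The Blinding paragraph is the only place where blocking is mentioned.

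**The concern.** The reason given does not support the access given. A therapist needs to be told one patient's assignment after it exists. The block size plays no part in that message. What the block size does provide, when combined with the record of past assignments, is knowledge of assignments not yet made.

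That knowledge sits with a person who also has contact with the referring team. Several entry steps involve discretion: providers may refer a patient or pass on contact details, and study staff make outreach calls and attend treatment groups. If knowledge of the next assignment influenced who was encouraged, or when a baseline visit was booked, the arms could differ before treatment begins.

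The planned effect sizes are adjusted for baseline scores (Section 7), which helps with imbalance in what is measured. Table 2 lists no measure of treatment motivation. Motivation could plausibly affect both session completion (Aim 1) and drinking outcomes (Aim 2), and adjustment could not remove an imbalance in it.

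**Working it through.** The plan gives no figure on predictability, so there is none to reproduce. The check asks how much a person learns from the block size and the full assignment history.

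**Inputs**
- Known to the investigator: block size and all past assignments (Section 4, Blinding).
- Number randomized: 80 (Section 4).
- Block size *b*: not stated. Assumed fixed, from 2 to 10.
- Ratio: not stated. Assumed 1:1, without stratification.

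**Allocations certain in advance.** An allocation is certain once one arm has used all its *b*/2 places in the block. The expected number per block is *b*/(*b*/2 + 1), so the share is 1/(*b*/2 + 1).

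**Allocations guessed correctly.** The best strategy is to guess the arm with more places left. The expected number correct per block is *b*/2 + ½(2^*b* / C(*b*, *b*/2) − 1).

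**Worked case, *b* = 4.** The chance of a correct guess at each position is:
1. First: 1/2.
2. Second: 2/3, because the other arm has two of the three remaining places.
3. Third: the first two match with probability 1/3 (guess certain) and differ with probability 2/3 (guess 1/2), giving 1/3 + 1/3 = 2/3.
4. Fourth: 1.

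The sum is 2.833, and 2.833/4 = 70.8%. Certain allocations: the fourth always and the third with probability 1/3, so 1.333/4 = 33.3%. Both agree with the formulas.

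| Assumed block size | Certain in advance | Average number of 80 | Best guess correct |
|---|---|---|---|
| 2 | 50.0% | 40.0 | 75.0% |
| 4 | 33.3% | 26.7 | 70.8% |
| 6 | 25.0% | 20.0 | 68.3% |
| 8 | 20.0% | 16.0 | 66.6% |
| 10 | 16.7% | 13.3 | 65.3% |
| Ideal concealment | 0% | 0 | 50% |

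Larger blocks reduce the problem without removing it: at *b* = 20 the figures are 9.1% and 61.7%. Section 4 also plans to recruit 115 people to reach 80. If all 115 were randomized, the percentages would stand and the certain allocations would number 57.5 (*b* = 2) to 19.2 (*b* = 10).

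**Do the existing blinding rules offset this?** Keeping the assessor unaware of condition, and the investigator unaware of outcomes, guards against biased measurement after randomization. Neither rule governs who reaches randomization or in what order. No other section supplies a concealment step.

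**The case against.** The best defence is that the investigator has little means of using the knowledge.

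- The stated meeting role is limited to reminders, progress updates and answering questions. The protocol does not say that individual referrals are discussed there.
- All residential patients receive a flyer and the screener at intake, patients may contact the team themselves, and the screener results reach the investigator de-identified.
- A research assistant runs the eligibility screen. Nothing in the protocol has the investigator choosing, consenting or declaring anyone eligible.
- The certainty concerns the next person *randomized*, not the next person *referred*. Between the two come up to three phone attempts, the phone screen, the baseline visit and, for some, a night of Holter monitoring. Several candidates may be in progress at once, so the order can change.
- Insomnia severity, drinking and alcohol problems are measured at baseline and enter the adjusted effect sizes.

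All of this stands. It makes the route of influence indirect, and it means that the percentages describe predictability rather than bias in any outcome. They would translate fully into steering only if the person guessing also controlled the order of entry. It does not supply a reason for the investigator to hold the block size, or replace a concealment procedure.

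A reader might go further in three ways that the documents do not support. First, that promised concealment has been broken: the protocol never promises it. Second, that the whole sequence can be deduced: only a share can. Third, that the diary week used to confirm insomnia after baseline lets the investigator remove people whose assignment is known: the protocol does not say that anyone is removed at that step.

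**Conclusion.** The point holds as a weakness in the allocation procedure. Allocation concealment is not described, and one stated rule gives a person with an indirect recruitment role more information than the stated purpose requires. For assumed fixed 1:1 blocks of 2 to 10 without stratification, about one half to one sixth of allocations would be known in advance.

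That the block size is disclosed is plain from the text. The size of the effect depends on the assumed block size, ratio and absence of stratification. Selection bias is a risk only: the documents do not show that it has occurred or how large it would be. In a single-site pilot of 80, where a few steered entries could matter, the cheap remedy is worth adopting.

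**What to change.** 1. Delete the reference to block size from the Blinding statement, so that the investigator is unblinded only to assignments already made.
2. Use randomly varying block sizes, not disclosed to the investigator or to anyone who recruits or screens. Varying them achieves nothing if each size is known.
3. Name the holder of the sequence: an existing team member with no recruitment, screening, outcome-assessment or analysis role, or a password-protected automated list. The co-investigator who receives outcome data for analysis (Section 12) is not a suitable holder.
4. Keep randomization after baseline, as Section 4 already has it. Add that assignments are released one at a time once baseline eligibility and measures are complete, and that the investigator is told each one only then.
5. If enrolment has begun, apply this to the remaining allocations and report what was known for the earlier ones.

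The cost is about one paragraph of protocol text, a regenerated list and some administrative work, with a slightly larger possible imbalance between arms. Whether extra staff time is needed depends on a suitable holder, or an automated list, being available. Some predictability may remain: the investigator still learns past assignments, so guesses could stay somewhat above 50%.
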